	
fatigue, and myalgia for 7 days following each study treatment (for Days 1-3, Days 4-7 and Days 1-7).
 
• Frequency, duration, intensity, duration, and relatedness of unsolicited AEs through to Day 57. Frequency of Serious Adverse Events (SAEs), Medically-Attended Adverse Events (MAAEs), and any AEs leading to study withdrawal (including decision by the Principal Investigator (PI) not to proceed with the second dose) at any time during study through to Day 394. Frequency and intensity of unsolicited AEs through to Days 57, 209, and 394 
Primary Immunogenicity Endpoints:
 
• Geometric mean titre (GMT) of the serum antibody response to the Sclamp antigen compared to placebo by antigen specific ELISA at Day 29 (28 days after first dose) and Day 57 (28 days after second dose).• GMT of the serum NAb titres to SARS-CoV-2 virus compared to placebo by microneutralisation (MN) assay at Day 29 (28 days after first dose) and Day 57 (28 days after second dose). 
Secondary Immunogenicity Endpoints:
 
• Proportion of subjects with ≥ 4 fold increase in titre above baseline by ELISA at Days 15, 29, 43, 57, 209, and 394 post-vaccination compared to placebo.• Proportion of subjects with ≥ 4 fold increase in titre above baseline by MN assay at Days 15, 29, 43, 57, 209, and 394 post-first study treatment administration compared to placebo.• GMT of the serum antibody response to the Sclamp antigen compared to placebo by antigen specific ELISA at Days 1, 15, 29 (28 days after first dose), and Days 43, 57 (28 days after second dose) and Days 209 and 394 (6 and 12 months post-second dose respectively).• GMT of the serum NAb titres to SARS-CoV-2 virus compared to by MN assay at Days 1, 15, 29 (28 days after first dose), and Days 43, 57 (28 days after second dose) and Days 209, 394. 
Exploratory Immunogenicity Endpoints:
 
• Proportion of subjects experiencing laboratory confirmed SARS-CoV-2 infection and/or severity graded COVID-19 disease between Days 57 and 394 compared to placebo.• Proportion of subjects with titres of $\geq 1:80$ and $\geq 1:160$ by MN assay at Days 1, 15, 29, 43, 57, 209, and 394 compared to placebo.• Proportion of subjects with ≥ 10 fold increase in titre above baseline by MN assay at Days 1, 15, 29, 43, 57, 209, and 394 compared to placebo.• Proportion of subjects showing an increase in antigen specific CD4+ T-cells at Days 15, 29, 36, 43, and 57 compared to pre-vaccination for vaccine antigen dose versus placebo.

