Safety Measurements	
Safety will be assessed by measuring the frequency and intensity of local and systemic solicited AEs, unsolicited AEs, SAEs, and safety laboratory data for all subjects.
 
Solicited AEs will be assessed by the proportion (%) of subjects with solicited local and systemic AEs up to 7 days after each vaccination by symptom and intensity for the periods: Days 1-3, Days 4-7, and Days 1--7.
 
Unsolicited AEs will be assessed by the proportion (%) of subjects with any unsolicited AEs within 28 days after each treatment dose or until Day 57.
 
Proportion (%) of subjects with SAEs, medically attended AEs (MAAEs), and any AEs leading to study withdrawal or decision by the Principal Investigator (PI) not to proceed with the second dose will be collected from study start until study exit. A MAAE is defined as any AE that requires an unscheduled/unplanned (at the time of visit 1) medical appointment with a primary care physician, or any other health professional.
 
Solicited local and systemic AEs will be collected using electronic diary cards for 7 days following each vaccination dose. Subjects will be requested to take an oral temperature reading for the first 7 days after vaccination and to record other systemic and local AEs that may develop, as well as medication that they have received. Solicited local AEs include pain, redness, and induration at the injection site. Solicited systemic AEs include raised oral temperature (≥ 38 °C), chills, nausea, headache, fatigue, diarrhoea, and myalgia. All other AEs will be collected at specified safety follow-up visits (Days 8, 15, 36, 43, 57, 209, and 394).

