5.4 Study Endpoints

Primary Safety Endpoints:

- Frequency, duration, and intensity of solicited local adverse events (AEs), including pain, redness, and induration for 7 days following each study treatment (for Days 1-3, Days 4-7 and Days 1-7).
- Frequency, duration, and intensity of solicited systemic adverse events (AEs), including fever, nausea, chills, diarrhoea, headache, fatigue, and myalgia for 7 days following each study treatment (for Days 1-3, Days 4-7 and Days 1-7).
- Frequency, duration, intensity, duration, and relatedness of unsolicited AEs through to Day 57. Frequency of Serious Adverse Events (SAEs), Medically-Attended Adverse Events (MAAEs), and any AEs leading to study withdrawal (including decision by the Principal

Investigator (PI) not to proceed with the second dose) at any time during study through to Day 394. Frequency and intensity of unsolicited AEs through to Days 57, 209, and 394

Primary Immunogenicity Endpoints:

- Geometric mean titre (GMT) of the serum antibody response to the Sclamp antigen compared to placebo by antigen specific ELISA at Day 29 (28 days after first dose) and Day 57 (28 days after second dose).
- GMT of the serum NAb titres to SARS-CoV-2 virus compared to placebo by MN assay at Day 29 (28 days after first dose) and Day 57 (28 days after second dose).

Secondary Immunogenicity Endpoints:

- Proportion of subjects with ≥ 4 fold increase in titre above baseline by ELISA at Days 15, 29, 43, 57, 209, and 394 post-first study treatment administration compared to placebo.
- Proportion of subjects with ≥ 4 fold increase in titre above baseline by MN assay at Days 15, 29, 43, 57, 209, and 394 post-first study treatment administration compared to placebo.
- GMT of the serum antibody response to the Sclamp antigen compared to placebo by antigen specific ELISA at Days 1, 15, 29 (28 days after first dose), and Days 43, 57 (28 days after second dose) and Days 209 and 394 (6 and 12 months post-second dose respectively).
- GMT of the serum NAb titres to SARS-CoV-2 virus compared to by MN assay at Days 1, 15, 29 (28 days after first dose), and Days 43, 57 (28 days after second dose) and Days 209, 394.

Exploratory Immunogenicity Endpoints:

- Proportion of subjects experiencing laboratory confirmed SARS-CoV-2 infection and/or severity graded COVID-19 disease between Days 57 and 394 compared to placebo.

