9.15.2 Recording of Adverse Events

Adverse events will be recorded and evaluated for their seriousness, severity, and relationship to the study medication. Adverse events will be collected and documented during the course of the study by appropriately trained and delegated medical staff in the clinic, as well as via self-reporting from subjects using the electronic diary. For a period of 12 months following the last study vaccine administration, adverse events will also be documented, if reported. Adverse events will be followed-up until complete resolution, or until the Investigator judges it to be safe to discontinue follow-up.

The term “reactogenicity” refers to solicited signs and symptoms (“solicited AEs”) occurring in the hours and days following vaccination, to be collected by the subject or legal representative(s) for 7 consecutive days, using an electronic Diary (eDiary) or paper Diary card (Diary).

The following solicited local and systemic AEs are included in the e-Diary. Solicited local reactions include erythema, swelling, and pain at the injection site. Solicited systemic reactions include fatigue, fever, headache, myalgia/arthralgia, chills, diarrhoea, nausea/vomiting.

Upon review of the subject diary, if a solicited local or systemic AE has been reported with a severity Grade=3 (severe), then the site is to confirm with the subject whether medical assistance was sought, was concomitant medication taken, and collect information around the event and outcome to document a safety assessment. In the event that the additional information leads to a determination that the solicited AE is deemed a Serious Adverse Event (SAE), the site will record the solicited AE as an SAE and report the event following the SAE reporting guidelines and time frames.

Each solicited AE is to be assessed using the toxicity grading provided in the scoring system adapted from the FDA Guidance for Industry -Toxicity Grading Scale for Healthy Adults and Adolescent Volunteers Enrolled in Preventive Vaccine Clinical Trials.⁴ Solicited AEs will be recorded as mild, moderate or severe by study subjects.

Table 2. Toxicity Grading for Solicited Local (Administration Site) Adverse Events

Local Reactions to Injection	Mild (Grade 1)	Moderate (Grade 2)	Severe (Grade 3)
Pain (at the vaccination site)	Does not interfere with activity	Repeated use of non-narcotic pain reliever >24 hours or interferes with activity	Any use of narcotic pain reliever or prevents daily activity

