Subjects will be instructed to report the local and systemic solicited AEs in the electronic Diary (eDiary)/Diary card on a daily basis, preferably about the same time each day. The eDiary/Diary card will be reviewed and the subject interviewed by the investigator or designee at each study visit regarding the AEs. All AEs are to be followed up until resolution or a stable clinical endpoint is reached. Any solicited AE that meets the following criteria must be entered into the Adverse Event eCRF:

- Solicited local or systemic AEs leading to a subject withdrawing or being withdrawn from the study by the PI,
- Solicited local or systemic AEs that last beyond 7 days duration,
- Solicited local or systemic AEs that lead to the decision not to further vaccinate a subject,
- Solicited local or systemic AEs that meet the definition of an SAE.

Each AE is to be documented in the eCRF with reference to date of onset, duration, frequency, severity, relationship to study treatment, action taken with study treatment, treatment of event, and outcome. Furthermore, each AE is to be classified as being serious or non-serious. Changes in AEs and resolution dates are to be documented on the eCRF.

For the purposes of this study, the period of observation for collection of AEs extends from the time the subject gives informed consent until the last follow-up visit (Day 394). Follow-up of the AE, even after the date of therapy discontinuation, is required if the AE persists until the event resolves or stabilizes at a level acceptable to the investigator. An AE that occurs in the period from informed consent until vaccination is a non-treatment emergent AE. An AE that occurs in the period from vaccination until study exit is a Treatment Emergent AE (TEAE).

When changes in the intensity of an AE occur more frequently than once a day, the maximum intensity for the event should be noted. If the intensity category changes over a number of days, then those changes should be recorded separately (with distinct onset dates).

Specific guidelines for classifying AEs by intensity and relationship to study drug are given in Table 4 and Table 5.

Table 4. Classification of Adverse Events by Intensity

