11.1 Safety Measurements

Safety will be assessed by measuring the frequency and intensity of local and systemic solicited adverse events (AEs), unsolicited AEs, serious adverse events (SAEs), and safety laboratory data for all subjects. All solicited adverse events will be summarised according to the protocol defined severity grading scales. The proportion of subjects experiencing each adverse event will be presented for each symptom severity. Summary tables showing the occurrence of any local or systemic adverse event overall and at each time point will be presented.

Reactogenicity will be assessed by the proportion of subjects with solicited local and solicited systemic AEs up to 7 days after each vaccination and calculated for 3 time intervals after each vaccination: Days 1--3, Days 4--7, and Days 1--7. Post-administration solicited adverse events reported from Days 1-7 will be summarised by time interval, maximal severity and by vaccine group. The severity of solicited local adverse events, including injection site redness, swelling and induration will be summarised according to categories based on linear measurement: 2.5 to 5.0 cm, 5.1 to 10.0 cm and >10 cm.

Injection site pain and systemic reactions (except fever) occurring up to 7 days after each vaccination dose will be summarised according to “mild”, “moderate” or “severe”. Body temperature will be summarised by 0.5 °C increments from 36.0 °C up to ≥ 40 °C and will be reported by route of measurement.

Unsolicited AEs will be assessed by the proportion of subjects with any unsolicited AEs for 28 days after each vaccination.

The proportion of subjects with SAEs, TEAS, non-scheduled GP visits, unsolicited medically attended AEs, unsolicited AEs leading to study withdrawal or decision by the PI to discontinue with the second dose, will be collected from study start until study completion.

All spontaneously reported adverse events occurring during the study assessed by the Investigator as probably related, possibly related, or not related to vaccination will be recorded.

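### Section 11.1 limits medically attended AEs and AEs leading to withdrawal or no second dose to unsolicited events, against the primary safety endpoint, and the AE eCRF entry list omits medically attended solicited reactions

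*Protocol*

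**What the plan says.** **Endpoint.** Section 5.4 (repeated in the Synopsis) lists among the primary safety endpoints the frequency of "Medically-Attended Adverse Events (MAAEs), and any AEs leading to study withdrawal". It includes the investigator's decision not to give the second dose and runs to Day 394.

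**Definition.** The Synopsis, under Safety Measurements, states: "A MAAE is defined as any AE that requires an unscheduled/unplanned (at the time of visit 1) medical appointment". Solicited events are not excluded. The same Synopsis paragraph announces the proportions of subjects with MAAEs and with AEs leading to withdrawal or no second dose, again without restriction.

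**Analysis.** Section 11.1 gives the corresponding proportions as "unsolicited medically attended AEs, unsolicited AEs leading to study withdrawal or decision by the PI to discontinue with the second dose". SAEs and non-scheduled GP visits, in the same sentence, carry no such limit. Later in Section 11.1 a separate summary of AEs leading to a medically attended visit is planned, also without a limit.

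**Recording.** Section 9.15.2 introduces a list with "Any solicited AE that meets the following criteria must be entered into the Adverse Event eCRF". The four criteria are withdrawal, duration beyond 7 days, a decision not to vaccinate further, and meeting the SAE definition. For a Grade 3 solicited AE, the same section says "the site is to confirm with the subject whether medical assistance was sought". There is no such instruction for lower grades.

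**The concern.** Solicited local and systemic reactions are plausible reasons for a vaccinated subject to see a doctor in the first week or to be refused the second dose. They belong to the endpoint as defined, yet the analysis sentence excludes them from two of its components. Since the excluded events are post-vaccination reactions, any undercount would be expected to fall more on the active arms than on placebo. That is an inference, as the protocol gives no rates. Section 11.3 bases the choice of dose and regimen on a joint evaluation of safety and immunogenicity by dosage group, so the reader of the report needs to know which events these lines contain.

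**Working it through.** No sample-size, power or event-rate figure in the protocol bears on this point. The check sets the endpoint, recording rule and analysis rule side by side for each type of solicited event.

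**Step 1: can a solicited event count as unsolicited once it is in the eCRF?** Section 9.15.2.1 defines an unsolicited AE as one that was not solicited through the subject's eDiary and was spontaneously reported. A fever or swelling entered in the daily symptom form fails the first condition. Moving it to the AE eCRF does not relabel it.

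**Step 2: trace each case.**

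| Solicited AE that... | In the endpoint (5.4, Synopsis)? | Required in the AE eCRF (9.15.2)? | In the 11.1 proportion as worded? |
|---|---|---|---|
| leads to withdrawal | Yes | Yes | No |
| leads to no second dose | Yes | Yes | No |
| is medically attended, non-serious, lasts 7 days or less, and leads to neither of the above | Yes | No | No |

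The analysis wording fails in all three rows. The recording rule fails only in the third.

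**Step 3: other routes for the third row.**
- Section 9.10.7 has subjects enter doctor visits in the diary.
- Section 9.15.2.2 tells subjects to report any MAAE to the site, but its sentence on collecting details speaks of unsolicited AEs.
- Section 9.15.2 asks about medical help for Grade 3 solicited events, but escalates the event only if it proves to be an SAE.
- Section 11.1 counts non-scheduled GP visits. That count is not tied to an AE, and the MAAE definition also covers other health professionals.
- The unrestricted Section 11.1 summary of AEs leading to a medically attended visit is built from CRF terms, so it includes a solicited reaction only if someone entered it.

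The visit can therefore leave a trace, but no instruction requires it to become an MAAE record linked to the reaction.

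**Step 4: size.** Section 8.2 gives 24 subjects per active treatment group in each part. One subject omitted from a proportion is 1/24 = 4.2 percentage points, and two are 2/24 = 8.3 points. How many would be omitted cannot be derived from the protocol.

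**The case against.** The case for leaving this alone is that little information is lost. Section 9.15.2 requires eCRF entry of solicited AEs that cause withdrawal or a decision not to vaccinate further, so those data exist and could be tabulated. The eCRF list sets mandatory entries and does not forbid others. Section 9.15.1 treats AEs reported by contacting the site between visits as unsolicited, so a reaction phoned in as an MAAE might be handled that way, although Section 9.15.2.1 leaves this unclear. Every solicited reaction appears in the reactogenicity tables by symptom, interval, maximal severity and group. Safety analysis is descriptive, and no decision rule depends on these proportions. The SAP, not shown, supersedes the protocol where they differ and may define the tables correctly.

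Much of this stands, and it rules out stronger readings. A reader might infer that the recording rules themselves discard solicited events that stop dosing; Section 9.15.2 says the opposite. A reader might also infer that reaction-driven doctor visits vanish, or that the reported rates would be zero; the diary, the GP-visit count and the unrestricted summary contradict that.

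Two things survive. The protocol contradicts itself on components of a primary safety endpoint. Reactogenicity tables do not repair this, because they show symptom and grade, not whether care was sought or the second dose withheld. And while the SAP could correct the analysis wording, it cannot supply a link between a visit and a reaction that the site was never required to record.

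**Conclusion.** The point holds in two parts. First, Section 11.1 contradicts Section 5.4, the Synopsis definition of an MAAE and its own later summary by restricting MAAEs and AEs leading to withdrawal or no second dose to unsolicited events. Taken literally, it yields proportions that are not the stated endpoint, and two different MAAE counts within one section. Second, the eCRF entry list has a narrow gap: non-serious, medically attended solicited reactions lasting 7 days or less that lead to neither withdrawal nor stopped vaccination.

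Each omitted subject changes a group's proportion by 4.2 percentage points within a part. The number affected is unknown, and the expectation that active arms are affected more is a judgement. The documents do not support the conclusion that dose selection would be misled, since it rests on the whole safety and immunogenicity profile. The conclusion assumes that Section 11.1 is applied as written and that the SAP does not override it. The recording gap does not depend on the SAP.

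**What to change.** 1. In Section 11.1, delete the word unsolicited from both items, so that they cover medically attended AEs (solicited or unsolicited) and any AEs (solicited or unsolicited) leading to withdrawal or to the investigator's decision against a second dose. This matches Section 5.4 and the Synopsis.
2. In Section 9.15.2, add a fifth criterion for AE eCRF entry: solicited local or systemic AEs that are medically attended, at any grade.
3. At each diary review, reconcile doctor-visit entries with solicited events of every grade.

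The cost is one edited sentence, one added bullet and a short check at diary review. There will be a few more eCRF entries, and the reported MAAE rate may be slightly higher.

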11.2 Immunogenicity

Various approaches will be used in this study to assess the immunogenic response of the SARS-CoV-2 Sclamp vaccine in subjects: analysis of SARS-CoV-2 specific immune response via ELISA, analysis of domain specificity and immunoglobulin isotype induction via Luminex Assay, analysis of MN assessed via virus neutralisation, and ADCC via a bioluminescent reporter assay. Additionally, induction of poly-functional T-cells will be assessed via stimulation of PBMCs with vaccine specific antigen, and further analysed via various staining techniques coupled with multi-flow cytometry. While analysis of safety and tolerability is the primary outcome of this study, the combination of immunogenicity data collected will provide some indication of the potential efficacy of the vaccine for future studies to investigate further.

Seroconversion rate is defined as a minimum 4-fold rise in post-vaccination titre at Days 29 and 57 relative to Day 1. The baseline titres for serum antibody to Sclamp and MN titres to SARS-CoV-2 virus will be \leq LLOQ and will be imputed as $\frac{1}{2}$ LLOQ.

Blood samples will be collected at specified visits according to the Schedule of Assessments included in Section 4, and blood volumes will be collected according to Section 9.9.

The immunogenicity analyses will evaluate immunogenicity of SARS-CoV-2 Sclamp vaccine as measured by ELISA and MN assay.

Additional immunologic assays, including ADCC reporter assay and Luminex assay will be used to conduct further exploratory analysis to determine antibody isotypes, domain specificities and functions that may be correlated with protection.

Potential for seroconversion to trigger false positives on HIV testing will be assessed by assessing blood samples in a panel of point of care and investigative HIV detection diagnostics.

Serum samples will be analysed by Sponsor designated qualified laboratory personnel blinded to the treatment assignment and the visit. Please see Laboratory Manual for complete details.

11.3 Success Criteria

In the absence of formal statistical hypotheses, the study will not be declared positive or negative according to pre-determined rules. The selection of an appropriate vaccine dosage and regimen for future studies will be determined by the joint evaluation of the safety and immunogenicity profiles of each dosage group and dosage regimen.

11.4 Analysis Populations

11.4.1 Intent-to-Treat (ITT) Population (Full Analysis Set, FAS)

Includes all trial subjects that:

- Provide consent; and
- Are randomized.

The ITT Population will be used for all listings and demographic summaries, and will be listed according to the planned treatment.

